### 9.4.3 Blinding

This is an open-label study.

#### **9.4.4 Treatment Compliance**

MK-3866 IV infusion will be performed by a qualified designee. The qualified designee will visually inspect the infusion pump device prior and after IV infusion, to ensure that the subject has received the entire dose. Should an infusion dosing be interrupted or incomplete for any reason (e.g., distal occlusion, proximal air, infiltration, large droplet of study medication on the surface of the skin), the initial start and stop times of the infusion, as well as all reinitiating start and stop times of the infusion will be recorded. Additionally, the pre-and post-infusion bag weights will be recorded.

## 10 STUDY PROCEDURES

The Study Events Flow Chart ([Section 6](#)) summarizes the clinical procedures to be performed at each visit. Individual clinical procedures are described in detail below. Additional evaluations/testing may be deemed necessary by the Investigator and/or the Sponsor for reasons related to subject safety.

For this study, the blood collection for MK-3866 is the critical parameter and needs to be collected as close to the exact time point as possible. All other procedures should be completed as close to the prescribed/scheduled time as possible, but can be performed prior or after the prescribed/scheduled time.

Any nonscheduled procedures required for urgent evaluation of safety concerns take precedence over all routine scheduled procedures.

### 10.1 Safety Assessment

#### 10.1.1 Screening

Within 28 days prior to dosing, medical history and demographic data, including name, sex, age, race, ethnicity, body weight (kg), height (cm), BMI (kg/m^2) and history of tobacco use will be recorded. Each subject will have a physical examination, vital sign measurements (heart rate, blood pressure, temperature, and respiratory rate), 12-lead ECG, and the laboratory tests of hematological, hepatic and renal function and additional tests as noted in [Section 10.1.6](#).

#### 10.1.2 Physical Examination

A full physical examination will be performed as outlined in the Study Events Flow Chart ([Section 6](#)). Symptom-driven physical examinations may be performed at other times, if deemed necessary by the Investigator or designee.

#### 10.1.3 Vital Signs

Single measurements of body temperature, respiratory rate, blood pressure, and heart rate, will be measured as outlined in the Study Events Flow Chart ([Section 6](#)).

Vital signs may be taken at any other times, if deemed necessary. Blood pressure and heart rate measurements will be performed with subjects in a seated position for at least 1 minute, except when they are supine or semi-reclined because of study procedures and/or adverse events (e.g., nausea, dizziness) or if deemed necessary by the Investigator or designee.

Blood pressure and heart rate will be measured within 24 hours prior to Day 1 dosing for the predose time point. When scheduled postdose, vital signs will be performed within approximately 15 minutes of the scheduled time point.

#### **10.1.4 ECG Monitoring**

Triplicate 12-lead ECGs will be performed at screening and predose; single 12-lead ECGs will be performed as outlined in the Study Events Flow Chart ([Section 6](#)), at all other times.

Predose triplicate 12-lead ECGs will be measured within 24 hours prior to dosing. The average value from the triplicate 12-lead ECGs collected prior to dosing will be considered the baseline ECG.

Timing and recording technique for triplicate 12-lead ECGs will be standardized for all subjects. Subjects will be required to lie quietly in a supine position with minimal movement and minimal exposure to noise and other environmental stimuli prior to and during ECG extraction. ECGs will be interpreted, signed, and dated by the Investigator or his/her designee. The ECGs will be classified as normal, abnormal but not clinically significant, or having a clinically significant abnormality. In addition, ECG parameter values of ventricular rate, PR interval, QRS duration, and QT interval (corrected and uncorrected) from the automated reading will be noted on the case report form (CRF). All clinically significant findings will be recorded as AEs for subjects enrolled in the study. An average for QTcF interval will be calculated for each triplicate.

Single 12-lead ECGs will be performed within approximately 20 minutes of the scheduled time point. Single ECGs will be performed with subjects in a supine position for at least 5 minutes. All ECG tracings will be reviewed by the Study Physician or his/her designee.

A subject will be withdrawn from the study by the Study Physician if, in their medical judgment, ECG findings are present which make continued study participation not in the subject's best interest.

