Confinement in the CRU for severe RI				X-																	
Visit and Post-Trial Visit	X																				X

a. For details on Procedures, refer to [Section 10](#) and/or corresponding appendices.

b. Within 28 days prior to dosing.

c. All subjects who received at least one dose of MK-3866 will return to the Clinical Research Unit (CRU) approximately 14 days after the last dose for follow-up procedures, and to determine if any adverse events have occurred since the last study visit.

d. Check-in: Subjects will be admitted to the CRU on Day -2 or Day -1, at the time indicated by the CRU.

e. Symptom-driven physical examinations may be performed at other times, at the Investigator's or designee discretion.

f. To be performed only once as the last study procedure for each panel: at 24 hours post start of infusion for healthy controls (Panel D); 48 hours for subjects with mild and moderate RI (Panel A and B), and 72 hours for subjects with severe RI (Panel C), or prior to early termination from the study.

g. Baseline eGFR will be obtained by taking the mean of the eGFR obtained from screening and from historical values within a 3 months period from screening. If no historical measurement is available, a second baseline eGFR sample will be taken during the screening period ( $\geq 72$  hours apart) and the mean of the two values will be used for group assignment; the second baseline eGFR sample may be obtained at the time of check-in.

h. Triplicate 12-lead ECGs to be performed at screening and for predose ECG measurement. Single 12-lead ECGs to be performed for all postdose ECG measurements.

i. To be performed within 24 hours prior to dosing.

j. Samples for serum chemistry will be obtained following a fast of at least 8 hours; however, in case of discontinuations or rechecks, subjects may not have fasted for 8 hours prior the serum chemistry sample is taken. For subjects who are anuric, urine samples for urinalysis will not be collected.

- k. The plasma pharmacokinetic sampling time points will be completed at 24 hours post start of infusion for healthy controls (Panel D); 48 hours for subjects with mild and moderate RI (Panel A and B), and 72 hours for subjects with severe RI (Panel C).
- l. The 0.5 hour blood sample for MK-3866 pharmacokinetic should be collected at the end of the infusion.

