- c. There will be a period of at least 7 days between MK-3866 dosing in Period 1 and Period 2.
- d. Check-in: Subjects will be admitted to the CRU on Day -2 or Day -1, at the time indicated by the CRU.
- e. Symptom-driven physical examinations may be performed at other times, at the Investigator's discretion.
- f. To be performed on Day 4 or prior to early termination from the study.
- g. Triplicate 12-lead ECGs to be performed at screening and for predose ECG measurements. Single 12-lead ECGs to be performed all postdose ECG measurements.

- h. To be performed within 24 hours prior to dosing.
- i. Samples for serum chemistry will be obtained following a fast of at least 8 hours; however, in case of discontinuations or rechecks, subjects may not have fasted for 8 hours prior the serum chemistry sample is taken. For subjects who are anuric, urine samples for urinalysis will not be collected.
- j. IV infusion will start immediately following the end of the scheduled HD in Period 1.
- k. The predose sample should be collected after HD and prior to the start of the infusion.
- l. The 0.5 hour blood sample for MK-3866 should be collected at the end of the infusion.
- m. If the next scheduled HD must be initiated prior the 72 hours postdose, a sample for MK-3866 analysis will be collected prior to HD.
- n. Urine collection intervals are: pre-dose (spot collection), 0 - 4, 4 - 8, 8 – 12, and 12 - 24 hours postdose. Urine samples will be collected whenever possible, as subjects may not be able to produce urine at each interval. For subjects who are anuric, urine samples will not be collected.
- o. This sample should be drawn for planned analysis of the association between genetic variants in DNA and drug response. This sample will not be collected at the site if there is either a local law or regulation prohibiting collection, or if the IRB/IEC does not approve the collection of the sample for these purposes. If the sample is collected, leftover extracted DNA will be stored for future biomedical research if the subject signs the FBR consent. If the planned genetic analysis is not approved, but FBR is approved and consent is given, this sample will be collected for the purpose of FBR.
- p. All subjects who received at least one dose of MK-3866 will return to the Clinical Research Unit (CRU) approximately 14 days after the last dose for follow-up procedures, and to determine if any adverse events have occurred since the last study visit.

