#### Both Parts:

Each IV infusion will be administered over 30 minutes ( $\pm 5$  minutes).

Hour 0 will correspond to the start of the IV infusion.

The time at which the IV infusion starts and ends will be recorded.

The pharmacy at the CRU will provide the IV dose ready for infusion for each subject and for each study period.

Each IV infusion will be administered using an IV infusion pump system over 30 minutes ( $\pm 5$  minutes), while subjects are seated or in a semi-reclined position, except when a supine position is dictated by study procedures. Should the need arise to change the infusion rate (i.e., due to an adverse event), changes to the infusion rate and the times at which those changes are made will be documented.

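### The two-sided windows around the 0.5 h ECG and BP/HR allow the one end-of-infusion safety reading to be taken while the infusion is still running

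*Combined protocol and SAP*

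**What the plan says.** All references are to the combined protocol and SAP.

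- **Time zero and infusion (9.4.1).** "Each IV infusion will be administered over 30 minutes", with ±5 minutes allowed, and "Hour 0 will correspond to the start of the IV infusion". The 0.5 h column is therefore the nominal end of infusion.
- **ECG (10.1.4).** "Single 12-lead ECGs will be performed within approximately 20 minutes of the scheduled time point". Postdose ECGs are single, and the subject must be supine for at least 5 minutes.
- **Vital signs (10.1.3).** "When scheduled postdose, vital signs will be performed within approximately 15 minutes of the scheduled time point".
- **Order of priority (Section 10).** The PK blood draw is the critical procedure. Everything else is to be done as near to schedule as possible, "but can be performed prior or after the prescribed/scheduled time".
- **Flow charts (6.1 and 6.2).** The first postdose BP/HR is at 0.5 h, as is the first postdose ECG in Part 1 and Panel E Period 1. The next marks are at about 2 h for BP/HR and about 2 to 3 h for ECG; the column alignment of the extracted tables does not settle this exactly. The extracted Period 2 chart shows an ECG only before dosing, which may be an extraction fault.
- **PK sample.** Footnote l in 6.1 says "The 0.5 hour blood sample for MK-3866 pharmacokinetic should be collected at the end of the infusion", and footnote l in 6.2 is equivalent. Section 10.2.1 holds draws from 0 to 1 hour to ±5 minutes. The ECG and BP/HR marks at 0.5 h carry no such footnote.
- **Hemodialysis (6.2 footnote s; 10.1.5).** In Period 2, dialysis starts right after the 0.5 h draw.

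**The concern.** During a constant-rate infusion the concentration climbs quickly to its peak at the end and then falls more slowly. A window of equal length on both sides of that peak is therefore unequal in concentration: the early side costs far more than the late side. The protocol recognises this for the PK sample, which it ties to the end of infusion, but not for the safety readings in the same column.

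Secondary Objective 3 is safety and tolerability across degrees of renal impairment. Only one ECG and one BP/HR reading are scheduled at the end of infusion, and postdose ECGs are not replicated. If that reading is taken mid-infusion, it describes a lower concentration than its label suggests, although it lies inside the stated window.

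**Working it through.** The documents give no concentration at the window edges, so there is no stated figure to reproduce. The fractions below are model-based.

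**Inputs (7.2.2).** Healthy, 800 mg: AUC0-∞ 272 µM·h, Ceoi 97 µM. ESRD, 200 mg, projected: AUC0-∞ 202 µM·h, Ceoi 24 µM. They are coherent: 97 × 200/800 = 24.25, close to 24; 272/202 = 1.35 and 439/202 = 2.17, matching the stated margins of 1.3 and 2.2.

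**Earliest compliant times.** ECG: 30 − 20 = 10 min. BP/HR: 30 − 15 = 15 min. Both precede even a 25-minute end of infusion.

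**Elimination rate.** One compartment, constant-rate infusion of length T = 0.5 h: Ceoi = (AUC/T)(1 − e^(−kT)), so k = −ln(1 − Ceoi·T/AUC)/T.

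- Healthy: 97 × 0.5/272 = 0.1783; k = 0.393/h (half-life 1.76 h).
- ESRD: 24 × 0.5/202 = 0.0594; k = 0.1225/h (half-life 5.66 h).

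**Fraction of Ceoi.** During infusion (1 − e^(−kt))/(1 − e^(−kT)); afterwards e^(−k(t−T)).

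| Reading, T = 30 min | Healthy | ESRD |
|---|---|---|
| ECG, early edge (10 min) | 0.0634/0.1783 = 0.355 | 0.0202/0.0594 = 0.340 |
| BP/HR, early edge (15 min) | 0.0935/0.1783 = 0.525 | 0.0302/0.0594 = 0.508 |
| Either, 5 min early (25 min) | 0.847 | 0.838 |
| BP/HR, late edge (45 min) | 0.906 | 0.970 |
| ECG, late edge (50 min) | 0.877 | 0.960 |
| 2 h | 0.555 | 0.832 |
| 3 h | 0.375 | 0.736 |

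**Infusion length.** With T from 25 to 35 minutes, the early edge is 0.29-0.42 for ECG and 0.44-0.62 for BP/HR. If the infusion takes 35 minutes, even a reading exactly at 30 minutes precedes its end, at 0.86-0.87.

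**Average over the whole window.** If readings were spread evenly, the mean fraction would be 0.81 (healthy) and 0.83 (ESRD) for ECG, and 0.86 and 0.87 for BP/HR. The level passes one half at 14.3 min (healthy) and 14.8 min (ESRD), so (14.3 − 10)/40 to (14.8 − 10)/40, or 11-12%, of the ECG window lies below one half. None of the BP/HR window does.

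**Average over the late side only.** The mean is (1 − e^(−kw))/(kw), with w the window length. ECG, w = 20 min: 0.94 (healthy) and 0.98 (ESRD). BP/HR, w = 15 min: 0.95 and 0.98.

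**Sensitivity to a distribution phase.** Assumed: fast half-life 0.1-0.5 h, fast fraction 0.3-0.7, terminal half-life 1.76-12 h. Early edges become 0.35-0.50 (ECG) and 0.52-0.66 (BP/HR); late edges 0.55-0.90 and 0.60-0.92. The early side remains the worse one in most of this range. In the most extreme cases (fast half-life 0.1 h carrying 70%) the gap nearly closes for ECG, and for BP/HR it closes or slightly reverses (0.64-0.66 early, 0.60-0.66 late).

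**The case against.** The strongest reply is that the early edge is a corner case. Section 10 asks for procedures as near to schedule as possible, and that instruction governs. A reading 5 minutes early is still at 84-85% of Ceoi. This stands, and it limits the point to what the rule permits.

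Several stronger readings are tempting but unsupported:

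- **That early readings are likely.** Priority for the blood draw and 5 minutes supine fit an ECG just after the draw equally well.
- **That 0.5 h is the only informative reading near the peak.** It is the only one scheduled at the end of infusion, but on the projected ESRD figures the 2 h level is still about 83% of peak. With the assumed distribution phase and a terminal half-life of 5.7-12 h, it is 37-82%.
- **That the reading exists to detect effects at Cmax.** No section says so. Section 7.2.1 expects no change in Cmax with renal impairment, and the projected 24 µM is about one quarter of the 97 µM at 800 mg and one sixth of the 152 µM at 1200 mg in healthy subjects. Part of the tolerability text is redacted.
- **That timing would bias a comparison between panels.** The same windows apply to all panels, and Section 11.3 makes ECG and vital-sign summaries optional. No formal analysis of them is planned.
- **That the ECG problem extends to Period 2.** The extracted chart does not show a postdose ECG there.

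Adverse events are also monitored throughout, and extra vital signs are allowed. What survives is narrow: the safety readings lack the anchor already given to the PK sample in the same column.

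**Conclusion.** The point holds as a cheap improvement, not as an error that threatens the study. The windows allow a compliant reading during the infusion, at about one third (ECG) or one half (BP/HR) of the end-of-infusion concentration at the extreme early edge, against 88-97% at the late edge. These sizes rest on a one-compartment model and on the protocol's healthy and projected ESRD exposures. A rapid distribution phase would narrow the gap and, at the extreme, remove it for BP/HR. The typical loss is much smaller than the edge figures suggest. The consequence is confined to how informative the end-of-infusion readings are for Secondary Objective 3. A reader might infer that peak-related effects will be missed or that panels will differ through timing; the documents support neither.

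**What to change.** Extend footnote l in Sections 6.1 and 6.2 to the 0.5 h ECG (Part 1 and Panel E Period 1) and the 0.5 h BP/HR, with matching sentences in 10.1.3 and 10.1.4. Time these readings from the actual end of infusion and do not take them before it. Keep the existing lengths on the late side (about 20 minutes for ECG, about 15 for BP/HR) and the two-sided windows at later time points. Leave the order relative to the PK draw to the site.

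For Panel E Period 2, the sponsor needs to reconcile the 0.5 h BP/HR window with 6.2 footnote s and Section 10.1.5. Because dialysis starts right after the 0.5 h draw, a late but compliant reading would fall during dialysis and mix its effect with that of the drug.

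The cost is a few sentences and slight crowding of procedures at the end of infusion. No visit, assessment or subject is added. Under the one-compartment model with evenly spread readings, the average level sampled would rise from 81-83% to 94-98% of Ceoi for ECG and from 86-87% to 95-98% for BP/HR.

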#### **10.1.5 Hemodialysis (ESRD Subjects Only)**

ESRD subjects on HD will receive HD as per their regular schedule and blood and dialysate sampling be collected as outlined in the Study Events Flow Chart ([Section 6](#)).

Dosing in Period 1 will occur immediately following completion of a normally scheduled HD session. For subjects following a Monday, Wednesday, Friday HD schedule, MK-3866 will be administered immediately following their Friday HD session. For subjects following a Tuesday, Thursday, Saturday HD schedule, MK-3866 will be administered immediately following their Saturday HD session. The 72-hour HD (either Monday or Tuesday) should initiate immediately following the 72-hour blood draw. If HD must be initiated prior to 72 hours postdose, a sample for MK-3866 analysis will be collected prior to HD, and the time recorded.

Dosing in Period 2 will occur approximately 30 minutes prior to the normally scheduled HD session. For subjects following a Monday, Wednesday, Friday HD schedule, MK-3866 will be administered prior to their Friday HD session. For subjects following a Tuesday, Thursday, Saturday HD schedule, MK-3866 will be administered prior to their Saturday HD

session. The subsequent HD session should initiate immediately following the 30 minute blood draw.

In Period 2, the HD period will be approximately 4 hours for all subjects. Blood samples collected during HD will be collected from both the pre-dialyzer and post-dialyzer blood lines.

The blood flow, dialysate flow, and the make and model of the dialyzer will be recorded.

### 10.1.6 Laboratory Tests

All tests listed below will be performed as outlined in the Study Events Flow Chart ([Section 6](#)). In addition, laboratory safety tests may be performed at various unscheduled time points, if deemed necessary by the Investigator.

#### Hematology

- Hemoglobin
- Hematocrit
- Total and differential leukocyte count
- Red blood cell count
- Platelet count

#### Serum Chemistry\*

- Blood urea nitrogen
- Bilirubin (total and direct)
- ALP
- AST
- ALT
- Albumin
- Sodium
- Potassium
- Chloride
- Glucose (fasting)
- Creatinine\*\*

#### Urinalysis §

- pH
- Specific gravity
- Protein\*\*\*
- Glucose
- Ketones
- Bilirubin
- Blood\*\*\*
- Nitrite\*\*\*
- Urobilinogen
- Leukocyte esterase\*\*\*

#### Additional Tests

- HIV test
- HBsAg
- HCV
- Urine or saliva drug screen
  - Opiates
  - Amphetamines
  - Barbiturates
  - Benzodiazepines
  - Cocaine
  - Cannabinoids
- Urine or breath alcohol screen
- Urine or saliva cotinine test
- Serum pregnancy test (for females only)
- FSH (for postmenopausal females only)

\* Serum chemistry tests will be performed after at least an 8-hour fast; however, in case of discontinuations or rechecks, subjects may not have fasted for 8 hours prior to the serum chemistry sample is taken.

\*\* At screening, eGFR will be calculated based on MDRD for renal classification assignment. Baseline eGFR will be obtained by taking the mean of the eGFR obtained from screening and from historical values within a 3 months period from screening. If no historical measurement

is available, a second baseline eGFR sample will be taken during the screening period ( $\geq$  72 hours apart) and the mean of the two values will be used for group assignment; the second baseline eGFR sample may be obtained at the time of check-in.

\*\*\* If urinalysis is positive for protein, blood, nitrite and/or leukocyte esterase, a microscopic examination (red blood cell, white blood cell, bacteria, casts, and, epithelial cells) will be performed.

§ Any unexplained drug-related hematuria or evidence of triphosphate crystals should be referred to a nephrologist.

#### 10.1.7 Assessing and Recording Adverse Events

An adverse event is defined as any untoward medical occurrence in a patient or clinical investigation subject administered a pharmaceutical product and which does not necessarily have to have a causal relationship with this treatment. An adverse event can therefore be any unfavorable and unintended sign (including an abnormal laboratory finding, for example), symptom, or disease temporally associated with the use of a medicinal product or protocol-specified procedure, whether or not considered related to the medicinal product or protocol-specified procedure. Any worsening (i.e., any clinically significant adverse change in frequency and/or intensity) of a preexisting condition that is temporally associated with the use of the Sponsor's product, is also an adverse event.

Changes resulting from normal growth and development that do not vary significantly in frequency or severity from expected levels are not to be considered adverse events. Examples of this may include, but are not limited to, teething, typical crying in infants and children and onset of menses or menopause occurring at a physiologically appropriate time.

Sponsor's product includes any pharmaceutical product, biological product, device, diagnostic agent, or protocol-specified procedure whether investigational or marketed, manufactured by, licensed by, provided by or distributed by the Sponsor for human use.

Adverse events may occur during clinical trials, or as prescribed in clinical practice, from overdose (whether accidental or intentional), from abuse, and from withdrawal.

For allocated subjects only, all adverse events that occur after the consent form is signed but before allocation must be reported by Investigator if they are the result of a protocol-specified intervention, including but not limited to washout or discontinuation of usual therapy, diet treatment, or a procedure. From the time of allocation through 14 days following cessation of treatment, all adverse events must be reported by the Investigator. Such events will be recorded at each examination on the Adverse Event case report forms/worksheets. The reporting timeframe for adverse events meeting any serious criteria is described in [Section 10.1.7.3.1](#). The Investigator will make every attempt to follow all subjects with non-serious adverse events for outcome. Any unexplained drug-related hematuria or evidence of triphosphate crystals should be referred to a nephrologist.

Electronic reporting procedures can be found in the Electronic Data Capture (EDC) data entry guidelines. Paper reporting procedures can be found in the Investigator Trial File Binder (or equivalent).

